Abstract	6
List of acronyms.....	6
AIM: main objective/research question	7
Secondary Objectives/research questions.....	7
Introduction.....	7
Background:.....	7
Justification:.....	7
Methodology	7
A. Study Design.....	8
B. Study period and context.....	8
C. Reference Population.....	8
D. Subject Inclusion/exclusion criteria.....	8
E. Intervention and Follow-up.....	8
F. Collection of biological samples and information	10
Statistical methodology	11
A. Data base	11
B. Study Variables.....	11
C. Sample Size	12
D. Statistical data analysis	12
Work plan	13
Ethical issues.....	13
Funding.....	15
ANNEX 1. Estimation of the research Project marginal costs	Error! Bookmark not defined.
Insurance	15
Publication and diffusion	15
References.....	15

Abstract

To evaluate the influence of ovarian stimulation for IVF / ICSI on the blood flow in the arteriae uterinae as well as whether there is an influence of the type of endometrial preparation for frozen embryo transfer (FET) with either hormonal replacement therapy or natural cycle on the blood flow of the arteria uterina left / right. Blood flow in the arteriae uterinae will be measured by Doppler ultrasound and calculating the pulsatility index (PI) and resistance index (RI).

Until now, it is not clear, whether hormonal stimulation for IVF / ICSI and administration of estradiol tablets in the context of preparing the endometrium for embryo transfer will influence the blood flow in the aa. uterinae at all. Until now, the optimal means of endometrial preparation for "Frozen Embryo Transfer" cycle is not clear and study results are contradictory. It is known, that there are remarkable differences in the endocrinological milieu between natural cycles and hormonal replacement cycles.

This study will measure the blood flow in the aa. uterinae in women, undergoing firstly ovarian stimulation for IVF / ICSI and later either HRT or NC for FET.

List of acronyms

ICSI	Intracytoplasmic sperm injection
IVF	In vitro fertilization
A.	Arteria
aa.	arteriae
PI	Pulsatility Index
RI	Resistance Index
FET	Frozen Embryo Transfer
NC	Natural Cycle
HRT	Hormonal Replacement Cycle
GnRH	Gonadotropin-Releasing-Hormone

AIM: main objective/research question

The primary aim of this observational prospective study is to evaluate, whether there is a difference in the blood flow, calculated as PI and RI in the arteriae uterinae right / left between women, undergoing HRT- or NC-cycle for FET. Measurements on the day of cycle start and the day of progesterone rise in NC-cycles / start of progesterone administration in HRT-cycles (+/- 1 - 2 days) will be performed.

Secondary Objectives/research questions

- To evaluate differences (delta) between the mean PI (between right and left A. uterine) and mean RI (between right and left A. uterine) on the day of cycle start and the day of ovulation induction - 1 - 2 days
- To compare thickness of the lining between HRT or NC.
- To compare number of days of estradiol exposure before the embryo transfer between HRT or NC.

Introduction

A. Background:

A wide spectrum of different factors, including uterine receptivity and endometrial thickness (Abdalla et al, 1994; Noyes et al, 1995) and endometrial texture (Bakos et al, 1993), have been implicated as crucial factors in implantation. It has also been suggested that uterine receptivity is related to the uterine blood flow. Due to the availability of ultrasound Doppler measurements, the uterine blood flow can be assessed non-invasively by transvaginal Doppler ultrasonography.

It is also known, that there are remarkable differences in the endocrinological milieu between natural cycles, ovarian stimulation cycles for IVF / ICSI and hormonal replacement cycles. Those differences may lead to different flow pattern in the vessels, providing blood supply to the uterus.

Until now, there are no data whether there is a difference in the blood flow of the aa. Uterinae .

B. Justification:

Until now, the changes in the blood flow of the aa. uterinae during hormonal stimulation for IVF / ICSI as well as during the preparation for FET are unclear. Additionally, the "best" approach to prepare the endometrium and further on to perform a frozen embryo transfer is still not clear and the data are contradictory. This study will evaluate whether there is any change in blood flow during hormonal stimulation for IVF/ICSI and during different types of endometrial preparation for FET. In case this study would show that the blood flow of the arteria uterina right and left is influenced negatively by one of the approaches, used for endometrial preparation of the FET, then this should be taken into account in future when deciding for one or the other approach.

Methodology

A. Study Design

- Prospective cohort study, observational and unicentric (in IVIRMA Middle East Fertility Clinic, Abu Dhabi, UAE).

B. Study period and context

- Patients who are treated for primary / secondary infertility in IVIRMA Middle East Fertility Clinic, Abu Dhabi, UAE
- Estimated study duration: 6 - 8 month
- Study would start after approval of the study protocol by EC of IVIRMA Middle East Fertility Clinic Abu Dhabi.
- Study would end after inclusion of the number of patients, estimated due to the sample size calculation

C. Reference Population

Pat. with primary / secondary infertility, who undergo an ovarian stimulation treatment for IVF/ICSI and subsequently are planned for FET with vitrified embryos, either as HRT-FET or as NC-FET

D. Subject Inclusion/exclusion criteria

Inclusion criteria:

- Patients who undergo ovarian stimulation in a GnRH-antagonist protocol for IVF / ICSI
- Patients who have vitrified embryo(s)
- Preparation for FET either in HRT or NC cycle

Exclusion criteria:

- Poor responder according to Bologna criteria (Ferraretti et al.) as follows:
- At least two of the following three features must be present:
 - (i) Advanced maternal age (≥ 40 years) or any other risk factor for POR;
 - (ii) A previous POR (≤ 3 oocytes with a conventional stimulation protocol);
 - (iii) An abnormal ovarian reserve test (i.e. AFC, 5–7 follicles or AMH, 0.5 –1.1 ng/ml).
- Uterine surgery for removal of fibroids (hysteroscopic, laparoscopic) or removal of uterine septum
- Endometriosis
- Asherman-Syndrome
- Previous cytotoxic treatment
- Previous radiation of the uterus / adnexal region
- Known hypertension
- Intake of Aspirin or similar medication which might influence the blood flow
- Status after tubal ligation
- Status after surgery in the adnexal region on 1 side

E. Intervention and Follow-up

- Patient will present themselves on day 2 / 3 of their period.

- Patients will undergo ovarian stimulation for IVF / ICSI in a GnRH-antagonist protocol: Start of stimulation medication (HMG, recFSH) on either day 2 or 3 of the cycle, dosage according to the ovarian response. From day 5 of stimulation a GnRH-antagonist will be added to prevent premature ovulation. Medication for ovulation induction (hCG, GnRH-agonist or dual trigger) will be given when at least 3 follicles are ≥ 17 mm.
- Patients will be planned for FET in either HRT or NC, according to the physician's decision.
- Factors to recommend HRT FET: irregular cycle, PCO, unavailability for treatment monitoring
- Factors to recommend NC FET: regular cycle 28 -33 days, availability for treatment monitoring

Endometrial preparation approaches:**Artificial (HRT) Cycles:**

- Commence E2 4mg from day 2/3 of period for 3 days
- Increase E2 to 6mg on day 4 of E2 treatment. E2 dose may be increased according to clinician discretion based on endometrial thickness.
- The patient will be scanned transvaginally throughout the HRT cycle to not only monitor endometrial development but to also exclude the presence of a dominant follicle on the ovaries.
- In conjunction with ultrasound monitoring the patient will undergo serial measurements of serum LH, estradiol and progesterone levels.
- Commence the initial progesterone dose of 100mg at 22hrs (vaginal suppository) after ≥ 10 days and ≤ 16 days of estradiol administration when the minimal endometrial thickness achieved is 6mm with a trilaminar appearance.
- Subsequently increase progesterone administration to 100mg vaginally three times daily. Continue estradiol administration 6mg (3 tablets daily). Embryo transfer is scheduled 5 days following the initial initiation of progesterone

Spontaneous natural cycles:

- Commencing on the second day of menses and intermittently throughout the patients' natural cycle ultrasound scans will be performed to monitor follicular growth.
- In conjunction with ultrasound monitoring the patient will undergo serial measurements of serum LH, estradiol and progesterone levels to accurately determine the timing of ovulation. These serum hormonal levels will be measured with an automated Elecsys® immunoanalyzer (Roche Diagnostics, Mannheim, Germany).
- The LH surge will be considered to have begun when the concentration rises by 180% above the most recent serum value and continues to rise thereafter (Irani et al. 2017, Fatemi et al., 2010).
- Day 1 after the LH rise, a decrease in estradiol concentration is identified. Twenty four hours later progesterone concentrations rise with a level of greater than or equal to 1.5nmol /L confirming ovulation (day 0) (Irani et al., 2017; Speroff et al.). This is considered as day 0 with initiation of vaginal progesterone 100mg (vaginal suppository) at 22pm that night. The following day (day 1) the patient increases progesterone administration to 100mg vaginally three times daily (8 hourly) and continues this regime until 7 weeks gestation as per clinic protocol. Embryo transfer is scheduled 5 days (day 5) following confirmation of ovulation (day 0).

For all study arms, transvaginal scan will be performed after the patient had emptied the bladder and is positioned in lithotomic position.

Measurement of the Doppler in the aa. uterinae:

A sagittal section of the uterus will be obtained and the cervical canal and internal cervical os will be identified. The transducer will be gently tilted from side to side and color flow mapping will be used to identify each uterine artery along the side of the cervix and uterus at the level of the internal os. Pulsed wave Doppler will be used with the sampling gate set at 2 mm to cover the whole vessel and care will be taken to ensure that the angle of insonation is less than 30°. When three similar consecutive waveforms are obtained, the PI and peak systolic velocity (PSV) will be measured and the mean PI of the left and right arteries calculated.

Images of the blood flow measurements will be taken and stored in an access-restricted folder. After completion of the study recruitment and data analysis, the images will be destroyed.

Timing for measurement of the Doppler in the aa. Uterinae will be performed:

- Ovarian stimulation cycle: day 2 or 3 of the cycle; day of ovulation induction or 1 to 2 days before in case patient will not be seen directly on the day of ovulation induction
- FET cycle:
- HRT: day 2 or 3 of the cycle and day of start of progesterone administration or 1 to 2 days before in case patient will not be seen directly on the day when she starts progesterone
- NC: day 2 or 3 of the cycle and day of start of progesterone rise or 1 to 2 days before in case patient will not be seen directly on the day when progesterone starts to rise

F. Collection of biological samples and information

No biological samples will be collected for this study

Statistical methodology

A. Data base

The database will be rigorously defined with the variables destined to be analyzed according to the objectives set. The necessary information will be exported from the clinical information manager, SIVIS, to a table in Excel format through a database-based query system. The data which is not recorded in SIVIS will be collected in a password-coded EXCEL file to guarantee the data protection.

The exported data will be duly codified in order to protect the clinical and personal information of the patients according to the applicable law in the place where the research project is carried out.

Finally, and prior to the statistical study, an exploratory data analysis will be carried out to review the quality of the information extracted.

B. Study Variables

EXPOSURE VARIABLES (INDEPENDENT)

- Type of endometrial stimulation. Categorical dichotomous variable (HRT or natural cycle)

MAIN-OUTCOME MEASURE (DEPENDENT)

- Difference in the blood flow, calculated as PI and RI, between the HRT- and the NC-FET cycles, on the day of progesterone administration / progesterone rise. Quantitative continuous variable

SECONDARY OUTCOME MEASURES (DEPENDENT)

- δ_{S11} : Continuous quantitative variable measured as the differences between average PI value on the day of cycle start and the day of ovulation induction - 1 - 2 days.
- δ_{S12} : Continuous quantitative variable measured as the differences between average RI value on the day of cycle start and the day of ovulation induction - 1 - 2 days.
- Thickness of the lining. Continuous quantitative variable measured in millimeters (mm).
- Number of days of estradiol exposure before the embryo transfer. Discrete quantitative variable.

CONTROL VARIABLES

- Cycles days before start of progesterone administration.
- In HRT cycles: amount (mg) of administered Estradiol.
- Age of the patient
- BMI of the patient
- Number of previous pregnancies
- Number of previous C-sections
- Number of previous miscarriages
- Smoker status: Smoking yes/no

C. Sample Size

So far, no study has been published evaluating the PI and RI of the arteria uterina between HRT- and NC-FETs.

The study of *Tekay et al.* compared the PI of the arteria uterina in a total of 57 patients in fresh ET's after ovarian stimulation and FET with HRT-preparation of the endometrium. However, this article does not study all the variables of our interest. Besides, it has low statistical power and our populations are different, so we consider that it is more convenient to carry out a pilot study to study descriptively the variables of interest in our population.

As this will be a pilot study, we plan to include 30 patients in each arm (HRT / NC), therefore we would estimate that we will have to include approximately 80 patients in total, as at the time of ovarian stimulation it will not be clear which type of FET patient will undergo later on. This approach was chosen in order not to interrupt patient recruitment. As this is expected to be a 2 : 1 recruitment (HRT : NC), an intra-group homogeneity analysis will be performed and if there are differences, patients from this group will be randomly selected for statistical analysis. Besides, in anticipation of potential participants wishing to withdraw from the study, an additional 5% of patients to the total sample will be added to cover possible losses, recruiting a total of 84 participants.

D. Statistical data analysis

EXPLORATORY DATA ANALYSIS

A statistical summary of the data collected in the study describing patient's population, cycle's most relevant parameters together with clinical results will be provided.

- Categorical variables will be presented in frequency tables, providing absolute frequencies and proportion of each level of each factor in the sample.
- Continuous variables will be summarized according the mean, standard deviation and 95%-confidence interval, all of them will be represented by diagrams or densities quartiles.

Exploratory data analysis will allow evaluating data quality and detecting anomalies.

HOMOGENEITY ANALYSIS

Although the inclusion criteria and study design tend to preserve the homogeneity of study, it is important to ensure comparability between groups for each control variable. Since each patient is assigned to a group according to clinical criteria and not by random assignment between groups, it will be important to perform a homogeneity analysis to ensure that the effect studied may be due to the type of endometrial preparation and not to the effect that may be caused by a control variable behaving differently between the two study groups.

Consequently, categorical variables will be compared using the χ^2 test, and for quantitative variables, a t-Student test will be applied (if we can assume normality, if it is not possible, we will use the Kruskal-Wallis test).

OBJECTIVE ASSESSMENT

To assess the primary objective, and considering the descriptive nature of any pilot study, confidence intervals of 90%, 95% and 99% will be provided for the blood flow level in each group, and for the difference

between the comparison groups. A basic comparison test will also be provided on an indicative basis. In order to do this, and considering the size of the sample, we will first apply tests of the normality of the data. If these tests are favourable, a t-Student test will be applied. In case of not being able to assume normality, we will apply a non-parametric test.

We will proceed in the same way for the rest of the secondary objectives.

Work plan

Phase I: drafting of protocol ([name], [name], [name]) and review / approval through UAGI and EC approval

Phase II: Patient recruitment and follow-up ([name], [name])

Phase III: Data analysis ([name], designated statistician from UAGI)

Phase IV: Drafting and reviewing of manuscript, submission and publication ([name], [name], [name], [name], [name])

	2019											
	Jan	Feb	Mar	Apr	May	Jun	Jul	Aug	Sep	Oct	Nov	Dec
Phase I												
Phase II												
Phase III												
Phase IV												
Phase V												

	2020											
	Jan	Feb	Mar	Apr	May	Jun	Jul	Aug	Sep	Oct	Nov	Dec
Phase I												
Phase II												
Phase III												
Phase IV												
Phase V												

Ethical issues

This Research Project respects the fundamental principles of the Declaration of Helsinki, the Council of Europe Convention on Human Rights and Biomedicine, the UNESCO Universal Declaration on the Human Genome and Human Rights, as well as the requirements of Health Authority Abu Dhabi, UAE, for protection of personal data and bioethics.

For the inclusion of all patients in the study, it is needed signed informed consent, which is approved by the Ethics Committee from the research centres

Funding

No funding needed

Needs funding	No	
Externally Funded project	No	Funding Institution Haga clic aquí para escribir texto.
External Funding plan (if no funding is available yet)	No funding needed	
IVIRMA Funding requested	Choose an item.	Internally Funded project
Funding time range		
Budget		

Insurance

IVIRMA Abu Dhabi has an Insurance Policy in force that conforms to current legislation and with coverage to compensate and indemnify cases of ill health or injury, which may arise in connection with their participation in the study, within routine clinical practice.

However for this observational study, no insurance is needed

Publication and diffusion

- Ultrasound in Obstetrics and Gynecology, IF 5.6
- Fertility and Sterility, IF 4.8
- ESHRE
- ASRM

References

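### The change in uterine-artery flow over the stimulated cycle has no unstimulated reference, so it describes that cycle and cannot show the influence of stimulation named in the Abstract

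*Combined protocol and SAP*

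**What the plan says.** **Purpose.** The Abstract states it causally: "To evaluate the influence of ovarian stimulation for IVF / ICSI on the blood flow in the arteriae uterinae". Introduction, B. Justification, states it descriptively: "This study will evaluate whether there is any change in blood flow during hormonal stimulation for IVF/ICSI".

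**Outcome.** Statistical methodology, B. Study Variables, defines delta_S11 as a "Continuous quantitative variable measured as the differences between average PI value on the day of cycle start and the day of ovulation induction", with the option of scanning 1 to 2 days earlier. Delta_S12 is the same for RI. The only exposure variable in that section is HRT versus natural cycle. Stimulated versus unstimulated cycle is not an exposure.

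**Analysis.** D. Statistical data analysis gives confidence intervals for each group and for the group difference, plus a test on an indicative basis. It handles the secondary objectives in the same way and calls the pilot descriptive.

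**Scans.** Methodology, E. Intervention and Follow-up, lists two scans in each cycle:
- "Ovarian stimulation cycle: day 2 or 3 of the cycle; day of ovulation induction or 1 to 2 days before"
- "NC: day 2 or 3 of the cycle and day of start of progesterone rise or 1 to 2 days before"

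**Sequence.** Each woman is followed while "undergoing firstly ovarian stimulation for IVF / ICSI and later either HRT or NC for FET". She has one type of FET cycle, not both.

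**The concern.** Introduction, A. Background, says that "there are remarkable differences in the endocrinological milieu between natural cycles, ovarian stimulation cycles for IVF / ICSI and hormonal replacement cycles" and that these may lead to different flow patterns. The contrast that bears on the influence of stimulation is therefore stimulated against natural, and the plan does not make it.

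A change from day 2/3 to the trigger contains any effect of stimulation plus whatever flow does between menses and mid-cycle without stimulation. If it is reported as influence, a normal cycle-phase change could be credited to stimulation. A stimulation effect in the opposite direction to the normal change could be hidden. A correctly paired pre-post analysis would not cure this, because the problem is the missing reference and not the test.

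**Working it through.** **1. What the planned change estimates.** Let S be the effect of stimulation and N the change an unstimulated cycle would show over the same interval.
- Mean of delta_S11 (or delta_S12) = S + N. Read as an estimate of S, its bias is N in full.
- HRT group minus NC group = (S + N in HRT women) − (S + N in NC women). If S and N are alike in the two groups, this is zero whatever S is. The planned grouping therefore does not isolate S.

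**2. Sample sizes (C. Sample Size).**
- The plan's total reproduces: 80 × 1.05 = 84.
- The plan gives no SD, effect size or power for PI or RI.
- At the expected 2:1 HRT:NC ratio, women with a natural cycle number 80/3 ≈ 27 (84/3 = 28), or 30 if the arm target is met.

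**3. How often a natural shift alone would look like an effect.** Assumptions: S = 0; all 80 women analysed together; paired t-test, two-sided 5%; N = d × SD of the within-woman change. The documents give no value of d, so a range is shown. Noncentrality = d√80.

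| d (assumed) | d√80 | Probability of significance |
|---|---|---|
| 0.1 | 0.89 | 0.14 |
| 0.2 | 1.79 | 0.42 |
| 0.3 | 2.68 | 0.76 |
| 0.5 | 4.47 | 0.99 |

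The nominal rate is 0.05. Equivalently, these are the chances that a 95% CI for the mean change excludes zero. Intervals computed within each FET group use fewer women and would exclude zero less often, but the bias is the same.

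**4. What the NC cycle can add.** For an NC woman, take D = change in the stimulated cycle − change in the NC cycle.
- 95% CI half-width = t(0.975, n−1)/√n, in SDs of D. For n = 27: 0.396. For n = 30: 0.373.
- In SDs of a single-cycle change, multiply by √(2(1−r)), where r is the correlation between the two changes and equal SDs in both cycles are assumed. For n = 27: 0.559 at r = 0 and 0.396 at r = 0.5.
- Difference detectable with 80% power, in SDs of D: 0.56 (n = 27) or 0.53 (n = 30).
- For comparison, the uncontrolled change in all 80 women has a half-width of 0.22 SD of that change.

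**5. Whether the two late scans match.** In the protocol's description of the natural cycle, estradiol falls on day 1 after the LH rise and progesterone rises 24 hours later, about two days after the LH rise. A scan on that day or 1 to 2 days before falls on or after the LH rise. The stimulated scan is on the trigger day or 1 to 2 days before, so never after the trigger. Hence D = S + (N up to trigger − N up to the surge or later) + any effect of cycle order. It equals S only if the last two terms vanish.

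**The case against.** The strongest reply is that the operative text is descriptive. The secondary objective asks only for differences between two time points, the Justification asks about any change during stimulation, and the analysis section stresses the descriptive nature of a pilot. The planned change answers that question, and the primary HRT-versus-NC comparison is untouched. This stands. A reader might infer that nothing can be learned about stimulation from these outcomes, but that goes too far: only the word influence is unsupported.

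The reply also bears on the remedy. A reader might infer that each woman's own natural cycle supplies the missing control. The documents do not support this:
- Only about a third of women at the expected ratio have a natural cycle.
- NC is recommended by the physician for regular 28 to 33 day cycles, while irregular cycles and PCO point to HRT, so NC women are a selected subset.
- Stimulation always comes first.
- The late scans lie on opposite sides of the surge or trigger.

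Reporting the difference of changes as the effect of stimulation would repeat the same kind of error.

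Finally, the percentages rest on assumed shifts and on a pooled paired test that the plan does not specify. That is so, and they are an illustration only. The precision is also modest: the half-width of 0.40 to 0.56 SD of a single-cycle change at n = 27 (r from 0.5 to 0) is wider than, or similar to, most of the assumed shifts.

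**Conclusion.** The point holds in a limited form. Delta_S11 and delta_S12 describe the change during the stimulated cycle. They do not support a statement about the influence of stimulation, because the natural-cycle change enters in full and no planned comparison removes it. Its size in this population is unknown from the documents. For assumed shifts of 0.2 to 0.5 SD, a null stimulation effect would appear significant in about 42% to 99% of studies of 80 women under the pooled paired test.

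The natural FET cycle offers a partial reference in about 27 to 30 women. It does not offer a causal estimate, and it does not serve the whole cohort. The primary objective is not affected. The change is worth making because it alters what may be concluded and needs no new data.

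**What to change.** 1. **Wording.** Reword the Abstract, or the conclusion to be drawn from delta_S11 and delta_S12, so that these outcomes are reported as the change during the stimulated cycle. This also aligns the Abstract with the Justification.
2. **Exploratory contrast.** In B. Study Variables and D. Statistical data analysis, add the following for women who have an NC-FET: the within-woman difference between the stimulated-cycle and NC-cycle changes in mean PI and mean RI, with its confidence interval and n. Call it a reference contrast.
3. **Stated limits.** Report with it that NC women are selected for regular cycles, that stimulation always comes first, that the NC late scan falls on or after the LH rise while the stimulated scan is at or before the trigger, and that precision is limited (half-width about 0.40 SD of the difference of changes at n = 27).

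The cost is protocol wording and one extra analysis of scans already scheduled. No additional patient or visit is needed.

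### The primary HRT-NC comparison uses neither the day 2/3 Doppler nor the time since stimulation, so a difference in flow already present when the FET cycle starts would be read as an effect of endometrial preparation.

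*Combined protocol and SAP*

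**What the plan says.** **Sequence and interval.** The Abstract describes women "undergoing firstly ovarian stimulation for IVF / ICSI and later either HRT or NC for FET". Methodology, C. Reference Population, covers women "who undergo an ovarian stimulation treatment for IVF/ICSI and subsequently are planned for FET with vitrified embryos, either as HRT-FET or as NC-FET". Neither place says how long after stimulation the FET cycle may begin. The only FET criterion in D. Subject Inclusion/exclusion criteria is "Preparation for FET either in HRT or NC cycle". The one time statement, in B. Study period and context, is "Estimated study duration: 6 - 8 month", which applies to the whole study and not to each woman.

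**Choice of arm.** E. Intervention and Follow-up states: "Patients will be planned for FET in either HRT or NC, according to the physician's decision". It continues: "Factors to recommend HRT FET: irregular cycle, PCO, unavailability for treatment monitoring". NC is favoured for regular cycles of 28-33 days and availability for monitoring.

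**Scans.** Section E schedules Doppler on day 2 or 3 of the stimulation cycle and near ovulation induction. It schedules it again on day 2 or 3 of the FET cycle and near the start of progesterone (HRT) or the progesterone rise (NC).

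**Outcomes and analysis.** In Statistical methodology, B. Study Variables, the main outcome is the HRT-NC difference in PI and RI on the progesterone day alone. The two secondary Doppler outcomes are changes from cycle start to ovulation induction. The only timing item among the control variables is "Cycles days before start of progesterone administration", which counts days within the FET cycle. In D. Statistical data analysis, the homogeneity analysis covers the listed control variables. The primary comparison is by confidence intervals and an unadjusted t-test or non-parametric test.

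**The concern.** Every participant has an exposure, ovarian stimulation, whose influence on uterine artery flow is one of the study's own questions. She is then scanned again in a later cycle to answer a different question. If flow at the start of that later cycle differs between arms for any reason, the unadjusted progesterone-day difference contains it. Two reasons are open on the text. The first is that the women differ, because arm is chosen on cycle regularity, PCO and availability. The second is that some effect of stimulation persists and the arms are scanned at different times after it.

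The plan accepts that assignment is not random and relies on the homogeneity analysis to guard against this. That analysis covers only listed variables, and time since stimulation is not among them. The Justification says an unfavourable finding for one approach should inform later choices between the two. A starting difference mistaken for a preparation effect would therefore matter even in a pilot.

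**Working it through.** **1. Is there a figure in the plan to reproduce?** There is none on this point: the plan gives no interval, no carry-over effect and no SD for PI or RI. The nearby recruitment total does reproduce (80 × 1.05 = 84) but does not bear on the question.

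**2. What does the crude difference contain?** For each woman let S be PI on day 2/3 of the stimulation cycle, F on day 2/3 of the FET cycle and P on the progesterone day. Then

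P = S + (F − S) + (P − F).

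Taking arm means and subtracting NC from HRT gives

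crude difference = [arm difference in S] + [arm difference in F − S] + [arm difference in P − F].

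- The first term is a difference between the women before stimulation.
- The second is what changed between the two cycle starts. Residual stimulation effects at FET start, if any, fall here.
- The third is the change during the FET cycle, which is where an effect of preparation would appear.

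The same identity holds for RI. It is exact when all three scans are available in the same women.

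**3. Which terms does the plan look at?** S, F and P are all scheduled in section E. The main outcome uses P only. The secondary changes use S together with the scan near ovulation induction, both in the stimulation cycle. F enters no defined outcome, although the statement of the primary aim mentions measurement at cycle start. The first two terms are therefore measurable but are neither reported by arm nor removed.

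**4. Would the interval be seen otherwise?** The listed control variables are cycle days before progesterone, estradiol amount, age, BMI, previous pregnancies, C-sections, miscarriages and smoking. None measures time since stimulation. The dates may well be in the clinic system, but the Data base section builds the export from the variables to be analysed.

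**5. What does adjustment cost at the planned size?** With 30 per arm, a two-group comparison has 60 − 2 = 58 residual degrees of freedom. Adding the FET-cycle baseline leaves 57, and adding the interval as well leaves 56. The crude standard error is SD × √(1/30 + 1/30) = 0.258 SD, so the 95% half-width is about 1.96 × 0.258 = 0.51 SD.

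**6. Would excluding women transferred early be a better check?** Suppose, purely for illustration, that 60% of HRT and 20% of NC women began FET at the first menses after retrieval. Dropping them leaves 30 × 0.4 = 12 and 30 × 0.8 = 24. The standard error becomes SD × √(1/12 + 1/24) = √0.125 = 0.354 SD. The estimate would then move by chance with a standard deviation of about √(0.125 − 0.0667) = 0.24 SD. A check that noisy could not distinguish carry-over from sampling variation.

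**The case against.** **A reader might infer that carry-over is established.** It is not. The Abstract says it is unclear whether stimulation influences flow at all, and the Background says only that different hormonal milieus may give different flow patterns. Both statements concern flow in the cycle in question. Nothing in the documents suggests an effect lasting beyond the next menses.

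**A reader might infer that HRT women are scanned sooner after stimulation.** The documents do not say so. Both preparations start from a bleed. Irregular cycles and PCO are steered to HRT, and infrequent bleeds could lengthen the HRT interval instead. Bias from carry-over needs both a residual effect and unequal intervals. With equal timing it is zero, and its sign is otherwise unknown. Any range in PI units would rest entirely on assumed inputs.

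**Trigger type.** The plan allows three options: "Medication for ovulation induction (hCG, GnRH-agonist or dual trigger) will be given when at least 3 follicles are ≥ 17 mm". It gives no ground for thinking that trigger differs by arm or alters flow in a later cycle.

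**It is a descriptive pilot with indicative tests.** This lowers the stakes. It does not clear the estimate, because the estimated difference and its intervals are the study's main product and a starting difference shifts both.

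**This is one part of a wider confounding problem.** That is fair: allocation by PCO and cycle regularity is the better documented source. It is also why baseline flow should be the main adjustment, with time since stimulation secondary.

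**Conclusion.** The point holds as a gap in the planned analysis, not as a demonstrated bias. It rests on the text alone: the interval is unlimited and unlisted, the arms are not randomised, the primary contrast is unadjusted, and the FET-cycle day 2/3 scan is scheduled but unused. As planned, the study could not separate a difference in flow present at FET start from an effect of preparation, although it will hold the scans needed to do so. Size and direction cannot be derived from the documents and no bias range should be quoted. Closing the gap is a worthwhile, low-cost improvement.

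One assumption matters. The FET-cycle day 2/3 scan serves as a baseline only if it precedes any effect of estradiol on flow. The plan starts estradiol on the same days and does not state the order.

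**What to change.** - **Statistical methodology, B. Study Variables:** add days from ovulation trigger to day 2/3 of the FET cycle as a control variable, so that the homogeneity analysis covers it. Trigger type may be tabulated by arm, descriptively.
- **Statistical methodology, D, Objective assessment:** report by arm the FET-cycle day 2/3 PI and RI, and the within-woman change from stimulation-cycle day 2/3 to FET-cycle day 2/3.
- **Same section:** beside the crude HRT-NC difference, give the difference adjusted by ANCOVA for FET-cycle day 2/3 PI (or RI). Add the interval as a further covariate in a sensitivity analysis. This last step addresses any effect of timing that is not visible at baseline.

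An analysis excluding women whose FET began at the first menses is not recommended, for the reason shown in the working.

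Cost: one exported field, slightly more analysis, and one or two degrees of freedom at about 30 per arm. No scans, visits or patients are added, and no change to FET scheduling is proposed. Baseline adjustment will not remove confounding by PCO or cycle regularity that acts during the FET cycle, and the report should say so.
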